### **8.1.2 Survival Follow-up**

Patients who have discontinued study intervention will be followed up for survival status Q12W until death, withdrawal of consent or the end of the study, ie, at the time of final analysis. Survival information may be obtained via telephone contact with the patient,

patient's family or by contact with the patient's current physician. In addition to the survival status, the assessment of anti-cancer and surgical treatments are also required.

Patients should be contacted in the week following the DCOs for the final analysis to provide complete survival data.

For patients who have not actively withdrawn consent, the status of those ongoing, withdrawn (from the study), and "lost to follow-up" at the time of the first analysis should be obtained by the site personnel by checking the patients notes, hospital records, contacting the patients general practitioner and checking publicly available death registries. In the event that the patient has actively withdrawn consent to the processing of their personal data, the vital status of the patient can be obtained by site personnel from publicly available resources where it is possible to do so under applicable local laws.

## **8.2 Safety Assessments**

Planned time points for all safety assessments are provided in the SoAs ([Table 1](#) and [Table 2](#)).

### **8.2.1 Physical Examinations**

A complete physical examination will be performed and include assessments of the following; general appearance, respiratory, cardiovascular, abdomen, skin, head and neck (including ears, eyes, nose and throat), lymph nodes, thyroid, muscular-skeletal (including spine and extremities) and neurological systems.

Physical examination will be performed at timelines as specified in the SoAs ([Table 1](#) and [Table 2](#)), investigators should pay special attention to clinical signs related to previous serious illnesses, new or worsening abnormalities may qualify as AEs, see [Section 8.3.4](#) for details.

### **8.2.2 Vital Signs**

Vital signs (heart rate, BP, temperature, and respiration rate) will be performed as specified in the SoAs ([Table 1](#) and [Table 2](#)) and as clinically indicated. Height will be assessed at the screening visit only. Weight will be assessed at the screening visit, Day 1 of each cycle for the first 6 cycles, Q8W from Cycle 7 onwards, and more frequently if clinically indicated. If a patient crosses over to savolitinib plus osimertinib they will continue to have follow-up assessments in line with these timings relative to randomisation, although they will be reported with a new baseline of the progression scan on randomised treatment (see [Section 8.1.1](#)).

- Temperature, pulse rate and BP will be assessed.
- Blood pressure and pulse measurements will be assessed in the semi-supine position with a completely automated device. Manual techniques will only be used if an automated device is not available.

- Vital sign measurements should be preceded by at least 10 minutes of rest for the patient in a quiet setting without distractions (eg, television, cell phones).
- Measurements will be taken in a semi-supine position after 10 minutes rest and will include temperature, systolic and diastolic BP and pulse.

Any changes in vital signs should be recorded as an AE, if applicable.

### **8.2.3 Electrocardiograms**

The QTCF evaluations will be done based on triplicate 12-lead ECGs as indicated in the SoAs (Table 1 and Table 2). Twelve-lead ECGs (triplicate) will be obtained after the patient has been rested in a supine position for at least 5 minutes. The investigator or designated physician will review the 12-lead ECGs. Electrocardiograms will be recorded at 25 mm/sec. All ECGs should be assessed by the investigator as to whether they are clinically significantly abnormal/not clinically significantly abnormal.

Triplicate ECGs will be required on Cycle 3 Day 1 collected pre-dose, and at 1, 3, 4, and 6 hours post-dose, on randomised treatment and again on cross-over treatment (Cycle 3 Day 1 on cross-over being relative to first dose of osimertinib), to coincide with collection of blood samples for assessment of PK of osimertinib and savolitinib at this visit.

If there is a clinically significant abnormal ECG finding, the investigator will record it as an AE on the eCRF. The original ECG traces must be stored in the patient's medical record as source data. A 28-day follow-up assessment will be required if an on-treatment assessment was abnormal at the time of discontinuation of study therapy, to confirm reversibility of the abnormality.

### **8.2.4 Multi-gated Acquisition/Echocardiogram**

An ECHO or MUGA scan to assess left ventricle ejection fraction will be conducted during the main study screening period, Q12W ( $\pm$  2 weeks) relative to randomisation, and at the end of treatment as indicated in the SoAs (Table 1 and Table 2). If a patient crosses over to savolitinib plus osimertinib they will continue to have follow-up assessments in line with these timings relative to randomisation, although they will be reported with a new baseline of the progression scan on randomised treatment (see Section 8.1.1). The modality of the cardiac function assessments must be consistent within a patient, ie, if ECHO is used for the screening assessment then ECHOs should also be done for subsequent testing. The patients should also be examined using the same machine and operator whenever possible, and quantitative measurements should be taken. A 28-day follow-up assessment will be required if an on-treatment assessment was abnormal at the time of discontinuation of study therapy, to confirm reversibility of the abnormality.

### **8.2.5 Clinical Safety Laboratory Assessments**

Blood and urine samples for determination of clinical chemistry, haematology, coagulation and urinalysis will be taken at the visits indicated in the SoAs (Table 1 and Table 2). All CSP-required safety laboratory assessments, as defined in Table 9, will be performed in a licensed local clinical laboratory according to local standard procedures.

The investigator should make an assessment of the available results with regard to clinically relevant abnormalities. The laboratory results should be signed and dated and retained at the centre as source data for laboratory variables.

For information on how AEs based on laboratory tests should be recorded and reported, see Section 8.3.5.

Additional safety samples may be collected if clinically indicated at the discretion of the investigator. The date, time of collection and results (values, units and reference ranges) will be recorded on the appropriate eCRF.

The clinical chemistry (including LFTs), haematology and urinalysis will be performed at a local laboratory at or near to the investigator site. Sample tubes and sample sizes may vary depending on the laboratory method used and routine practice at the site.

The following laboratory variables will be measured.

**Table 9 Laboratory Safety Variables**

Clinical chemistry	Haematology	Urinalysis (Dipstick) a
S/P – Albumin	B – Haematocrit	U – Blood
S/P – ALP b	B – Haemoglobin	U – Glucose
S/P – ALT b	B – Leucocyte cell count	U – Ketones
S/P – Amylase	B – Platelet count	U – Leukocyte esterase
S/P – AST b	B – Red blood cell count	U – Protein
S/P – Bilirubin, total b	B - Reticulocytes	
S/P – Calcium, total	B – Absolute leucocyte differential count: B – Neutrophil count B – Lymphocyte count B – Eosinophil count	
S/P – Creatinine		
S/P – Glucose		
S/P – Magnesium		
S/P – Sodium		
S/P – Potassium		
S/P – Total protein		
S/P – Blood urea nitrogen or urea		
S/P – Lactate dehydrogenase		

a If 3 + or greater proteinuria is identified by dipstick assessment, a 24-hours urine collection for formal quantification of the level of protein excretion should be performed

b Designates tests that are considered LFTs and are to be done weekly for the first 10 weeks relative to randomisation, then Day 1 of every subsequent cycle and at progression.

ALP = Alkaline phosphatase; ALT = Alanine aminotransferase; AST = Aspartate aminotransferase; B = Blood; LFT = Liver function test; P = Plasma; S = Serum; U = Urine.

**Note:** In case a patient shows an AST or ALT  $\geq 3 \times$  ULN together with TBL  $\geq 2 \times$  ULN please refer to [Appendix E](#) “Actions Required in Cases of Increases in Liver Biochemistry and Evaluation of Hy’s Law”, for further instructions.

### 8.2.6 Serum of Urine Pregnancy Test

A pregnancy test on urine or blood sample will be performed for pre-menopausal WOCBP, at the study screening visit, and prior to the first dose of study intervention on Cycle 1 Day 1, Day 1 of every cycle, and at treatment discontinuation. Tests will be performed by the institutional laboratory. If results are positive the patient is ineligible/must be discontinued from the study. In the event of a suspected pregnancy during the study, the test should be repeated and if positive, the patient will be discontinued from study intervention immediately.

### 8.3 Adverse Events and Serious Adverse Events

The Principal Investigator is responsible for ensuring that all staff involved in the study are familiar with the content of this section.

The definitions of an AE or SAE can be found in [Appendix B](#).

Adverse events will be reported by the patient (or, when appropriate, by a caregiver, surrogate, or the patient's legally authorised representative).

The investigator and any designees are responsible for detecting, documenting and recording events that meet the definition of an AE.

### **8.3.1 Time Period and Frequency for Collecting AE and SAE Information**

Adverse Events and SAEs will be collected from time of signature of the main study ICF throughout the treatment period and including the follow-up period. The follow-up period is defined as  $28 \pm 7$  days after study intervention is discontinued.

Procedure-related AEs and SAEs for those patients who provide a new tumour biopsy occurring up to and including 21 days after the new tumour biopsy procedure will be captured. This procedure may be performed prior to signing the main study ICF.

If the investigator becomes aware of a SAE with a suspected causal relationship to the investigational medicinal product that occurs after the end of the clinical study in a patient treated by him or her, the investigator shall, without undue delay, report the SAE to the sponsor.

### **8.3.2 Follow-up of AEs and SAEs**

Any AEs that are unresolved at the patient's last AE assessment in the study are followed up by the investigator for as long as medically indicated, but without further recording in the eCRF. AstraZeneca retains the right to request additional information for any patient with ongoing AE(s)/SAE(s) at the end of the study, if judged necessary.

#### **8.3.2.1 Adverse Event Variables**

The following variables will be collected for each AE:

- AE (verbatim)
- The date and time when the AE started and stopped
- The maximum on-treatment CTCAE grade (according to CTCAE Version 5.0)
- Whether the AE is serious or not
- Investigator causality rating against the study interventions (yes or no)
- Action taken with regard to study interventions
- Outcome.

In addition, the following variables will be collected for SAEs:

- Date AE met criteria for SAE
- Date investigator became aware of SAE
- AE is serious due to
- Date of hospitalisation
- Date of discharge
- Probable cause of death
- Date of death
- Autopsy performed
- Causality assessment in relation to study procedure(s)
- Causality assessment to other medication

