**Table 1 Schedule of Activities for Randomised Treatment**

Visit	Pre-screening	Screening	Intervention Period				Follow-up a			Details in CSP Section or Appendix	
			Cycle 1 (28-day cycle)				Cycles 2 to 6 (28-day cycle)	Cycle 7 onwards (28-day cycle)	Treatment discontinuation visit		28-Day follow-up visit b
Week (Day 1 of)	NA	-4 to 0	1 to 4				5 to 24	25 onwards		Within 7 days of the final dose of study intervention	
Study day		-28 to -1	1 to 28				29 to 168	169 onwards			
Day of cycle			1	8	15	22	1	1			
Visit window			± 1 day				± 3 days	± 3 days			
Survival follow-up											
Survival status										Q12W g	8.1.2

- a The follow-up period is only applicable for those who discontinue randomised treatment and do not cross-over to treatment with savolitinib plus osimertinib. Patients who cross-over are to carry on assessments as per the SoA in [Table 2](#).
- b As a minimum, telephone contact should be made with the patient 28 days following the discontinuation of study intervention to collect new AEs and follow up on any ongoing AEs and concomitant medications (including any subsequent cancer therapy, if appropriate).
- c At pre-screening, testing for MET amplified tumour by central FISH testing must be performed on an FFPE tumour specimen collected after progression of previous osimertinib treatment, which may or may not have been the most recent treatment. Testing may be performed as initial pre-screening with consent obtained using the Pre-screening ICF in advance of obtaining consent for the main study. Detailed sample requirements will be defined in study Laboratory Manual. MET amplified is defined as increased gene copy number. Samples > 2 years old will not be accepted. New tumour specimens should only be collected specifically for pre-screening for this study where the expected risk of an AE related to the procedure is < 2%.
- d EGFRm status is an inclusion criterion and part of disease diagnosis and a criterion to receive osimertinib; prospective central testing is not required.
- e Weight will be assessed as shown above and more frequently if clinically indicated.
- f Triplicate ECGs will be required on Cycle 3 Day 1 collected pre-dose and at 1, 3, 4 and 6 hours post-dose to coincide with collection of blood samples for assessment of PK of osimertinib and savolitinib at this visit.

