#### **9.4.3 Safety**

Safety and tolerability will be assessed in terms of AEs, SAEs, discontinuation rate due to AEs, deaths, laboratory data, vital signs, ECHO data, ECG data and ECOG performance status. All safety analyses will be performed on the SAS. Data will also be presented separately for patients who crossed over to savolitinib plus osimertinib upon investigator-assessed PD per RECIST 1.1 on savolitinib plus placebo. Safety data will be presented using descriptive statistics unless otherwise specified.

Adverse events will be coded using the most recent version of MedDRA that have been released for execution at AstraZeneca. Adverse events will be graded according to the National Cancer Institute CTCAE (Version 5.0).

The number of patients experiencing each AE will be summarised by the MedDRA system organ class, preferred term and treatment group. The number and percentage of patients with AEs in different categories (eg, causally related, CTCAE Grade  $\geq 3$  etc) will be summarised, and events in each category will be further summarised by MedDRA system organ class, preferred term and treatment group. If there are sufficient SAEs, they will be summarised separately. Further details will be provided in the SAP.

Adverse events occurring prior to the start of study intervention, treatment-emergent AEs and post-treatment emergent AEs will be presented separately. Adverse events occurring in the savolitinib in combination with placebo group will be split into 2 presentations based on whether they occurred before or after the crossover into the savolitinib in combination with osimertinib group.

Any AE occurring before the first dose of study intervention will be included in the data

listings but will not be included in the summary tables of AEs. Adverse event summary tables will include only treatment-emergent AEs. The following events are considered treatment emergent:

- Adverse events with an onset date on or after the first dose of randomised study intervention and within the safety follow-up period (28 days [ $\pm$  7 days] after last dose of all study intervention). Any events in this period that occur after a patient has received further therapy for cancer (following discontinuation of all study intervention) will be flagged in the data listings.
- Worsening of pre-existing events on or after the first dose of study intervention and within the safety follow-up period.

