Any events in this period that occur after a patient has received further therapy for cancer (following discontinuation of all study intervention) will be flagged in the data listings, but not included in the summaries.

An overview of AEs will present for each treatment group the number and percentage of patients with any AE, AEs with outcome of death, SAEs, and AEs leading to discontinuation of study intervention, as well as AEs leading to study intervention dose interruptions, and AEs leading to study intervention dose reduction as well as the number of individual occurrences in those categories.

Separate AE tables will be provided taken into consideration relationship as assessed by the investigator, CTCAE grade, seriousness, death and events leading to discontinuation of study intervention for the first 6 weeks and at any time as well as other action taken related to study intervention.

An additional table will present number and percentage of patients with most common AEs. Most common (eg, frequency of  $> x\%$ ,  $\geq x\%$ ) will be defined in the SAP.

In accordance with the requirements of the FDA, a separate table will present non-serious AEs occurring in more than 5% of patients in any treatment group.

Key patient information will be presented for patients with AEs with outcome of death, SAEs, and AEs leading to discontinuation of study intervention.

An AE listing for the SAS will cover details for each individual AE; an AE listing for patients who were not exposed to study intervention is presented separately.

Full details of AE analyses will be provided in the SAP.

During the evaluation of the AE data, an AstraZeneca medically qualified expert will review

the list of AEs that were not reported as SAEs or AEs leading to discontinuation. Based on the expert's judgement, significant AEs of particular clinical importance may, after consultation with the Global Patient Safety Physician, be considered other significant AEs and reported as such in the CSR. A similar review of laboratory/vital signs (pulse and BP)/ECG data will be performed for identification of other significant AEs. Examples of these could be marked haematological and other laboratory abnormalities, and certain events that lead to intervention (other than those already classified as serious), dose reduction or significant additional treatment. Tables and figures for potential Hy's Law cases will be produced.

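### The only AE severity variable is the maximum on-treatment CTCAE grade, but AEs are tabulated by grade up to 28 (±7) days after the last dose, so the two windows do not match

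*Supplement*

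**What the plan says.** Section 8.3.2.1 lists the variables to be collected for each AE. The only severity item is "The maximum on-treatment CTCAE grade (according to CTCAE Version 5.0". No onset, baseline or post-treatment grade is listed.

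Section 8.3.1 collects AEs from the main consent "throughout the treatment period and including the follow-up period", and sets follow-up at 28 ± 7 days after study intervention is discontinued. Footnote b of Table 1 requires at least a telephone contact 28 days after discontinuation "to collect new AEs and follow up on any ongoing AEs and concomitant medications".

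Section 9.4.3 treats as treatment-emergent "Adverse events with an onset date on or after the first dose of randomised study intervention and within the safety follow-up period", counted from the last dose of all study intervention. It adds "Worsening of pre-existing events on or after the first dose of study intervention and within the safety follow-up period". It then says: "Adverse event summary tables will include only treatment-emergent AEs". The tables include Grade 3 or higher as a category, and: "Separate AE tables will be provided taken into consideration relationship as assessed by the investigator, CTCAE grade, seriousness".

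**The concern.** The tables cover a longer window than the grade that feeds them. If sites follow Section 8.3.2.1 to the letter, an AE that is Grade 2 at the last dose and reaches Grade 4 a week later stays at Grade 2. An AE that starts a week after the last dose has no on-treatment grade at all. Both still count as treatment-emergent, so both enter the tables by grade. Worsening after the last dose is itself a treatment-emergent criterion, yet no listed grade variable would show it.

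Safety and tolerability is a stated objective, and the grade tables are one of its main summaries. A grade that was never entered cannot be recovered at the analysis stage, whatever the SAP says.

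**Working it through.** No figure in the plan depends on this point, so the check sets the sections side by side.

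**1. Length of the uncovered window.** If on-treatment ends at the last dose, the part of the treatment-emergent window without a grade is the safety follow-up: 28 − 7 = 21 days to 28 + 7 = 35 days.

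**2. What on-treatment means.** The protocol never defines it. Two pieces of usage point the same way:
- Section 8.3.1 names the treatment period and the follow-up period separately.
- Section 8.2.3 says "A 28-day follow-up assessment will be required if an on-treatment assessment was abnormal at the time of discontinuation of study therapy". Footnote g of Table 1 and Section 8.2.4 use the same construction. Follow-up there comes after on-treatment. These places concern ECG and cardiac imaging, so they are evidence of usage and not a rule for AE grades.

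**3. Whether other text supplies the missing grade.**

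| Place | What it settles | Period of the recorded maximum |
|---|---|---|
| 8.3.2.1 | Grade item for each AE | On-treatment |
| 9.4.3 | AEs are graded by CTCAE 5.0 | Not stated |
| Appendix B, intensity rating scale | Scale applies to all events with a CTCAE grading | Not stated |
| Appendix I 1 | AEs during the study are assessed by CTCAE 5.0 | Not stated |

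The last three name the scale and set no on-treatment limit. Only 8.3.2.1 says over what period the recorded maximum is taken. The text is therefore inconsistent, and sites could reasonably record in different ways.

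**4. Which events are exposed.** The follow-up clock starts at the last dose of all study intervention.
- In Table I2, interstitial lung disease leads to discontinuation of osimertinib, with savolitinib marked not applicable; hepatic events concern savolitinib, with osimertinib marked not applicable. Section 7.1 lets a patient continue on the other drug. Such a patient may still be on study treatment when the event peaks.
- A temporary hold does not clearly end the treatment period.
- The exposed cases are therefore mainly patients who stop all study intervention.

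**5. What is captured by another route.** Laboratory CTCAE grades are calculated from the values (9.4.3), and liver test monitoring continues after discontinuation for a liver test abnormality (Appendix I 3.2). Seriousness, outcome, hospitalisation and death have their own fields (8.3.2.1), and deaths are listed (9.4.3). Investigator-graded events such as skin reactions, hypersensitivity and lung events have no calculated grade behind them.

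**6. Whether the size can be estimated.** Table 3 gives hepatotoxicity of Grade 3 or higher as 11.5% in the savolitinib database. Suppose, purely as an assumption, that 10% to 30% of these reach Grade 3 only after the last dose:
- 11.5% × (1 − 0.10) = 10.4%; 11.5% × (1 − 0.30) = 8.1%.
- At the originally planned 28 per arm, which will not be reached: 28 × 0.115 = 3.2 patients, of whom 10% to 30% is 0.3 to 1.0.

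Nothing in the documents supports the 10% to 30%, and hepatotoxicity is the example best protected by calculated laboratory grades. This is an illustration of scale only.

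**The case against.** The case against is substantial. The term is undefined, and the list in 8.3.2.1 applies to every AE, including those collected in follow-up, so it can be read as expecting a grade for them. Section 9.4.3, Appendix B and Appendix I all call for grading without an on-treatment limit. Neither the eCRF nor the SAP is shown, and Section 9.4.3 leaves the full AE analysis detail to the SAP. Safety is descriptive only, and the study closed recruitment early.

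Most of this stands, and it rules out three stronger readings that a reader might infer:
- *That grades are certain to be lost.* This is the literal consequence of one bullet, against other text that asks for grading generally.
- *That the loss is systematic for the key toxicities because drug is stopped at their first sign.* Table I2 stops a single drug for lung and hepatic events, and Appendix I 3.2.1 continues dosing for some transaminase elevations.
- *That the arm with more discontinuations will look safer.* Truncation tied to discontinuation could differ between arms, but the documents give no basis for a direction or a size.

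What the objection does not remove is the mismatch. Naming a scale does not say when the maximum is taken. An eCRF that already covers the window would be a reason to correct the protocol wording, and the sponsor should check it.

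**Conclusion.** The point holds as an inconsistency between what is collected and what is tabulated. Under the plain reading of on-treatment, investigator-graded AEs that peak within 21 to 35 days after the last dose are under-graded, and those that start then have no on-treatment grade, although the plan tabulates both by grade.

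The effect is confined to descriptive grade tables and mainly to patients who stop all study intervention. Laboratory grades, seriousness, outcome and deaths are captured separately, and the primary ORR analysis is unaffected. No reliable magnitude can be given. The conclusion assumes that on-treatment ends at the last dose and that the eCRF follows the protocol list; if the eCRF already records the maximum through safety follow-up, only the wording needs repair.

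**What to change.** In Section 8.3.2.1, record the maximum CTCAE grade from the first dose of study intervention to the end of the 28 (±7)-day safety follow-up after the last dose of all study intervention, which is the treatment-emergent window of Section 9.4.3. For patients who cross over, take the maximum separately before and after cross-over.

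Both limits matter. AEs are collected from consent, so a maximum taken from AE onset would let in pre-dose grades. A single maximum across cross-over would assign a grade reached on the combination to an AE that began on savolitinib plus placebo, and so break the before/after split in Section 9.4.3.

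Align Section 8.3.2.1, Section 9.4.3 and Appendix B on this definition. Query AEs that were ongoing at, or began after, the last dose. Do this before the database closes to new data following the final data cut-off (Section 6.7), since unresolved AEs are not recorded further in the eCRF after the last AE assessment (Section 8.3.2).

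The cost is a short wording change in the protocol and eCRF guidance, a few extra queries, and possibly slightly less favourable severity figures.
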